requiring treatment following anti-toxin administration up to 90 days, occurrence of serotonin surge syndrome while on therapy.

Causal contrast of interest	Intention-to-treat effect; per-protocol effect.	Observational analog to Intention-to-treat effect and per-protocol effect.
Analysis plan	Intention-to-treat and per protocol effects estimated via comparison of adjusted 90 day in-hospital mortality risk assigned to each treatment strategy.	
Intention-to-treat and per protocol effects estimated via comparison of adjusted in-hospital mortality risk assigned to each treatment strategy.
 
To account for confounding by indication a propensity score (PS) will be generated based on the probability of receiving linezolid using the patient and center level variables selected a priori based on clinical judgment, . Overlap weighting on a propensity-score between the two groups will be performed with downstream adjustment for ICU stay , shock and debridement/source control.

Abbreviations: CDI: Clostridioides difficile infection; GAS: Group A streptococcus.

The study was designed in accordance with the trial emulation approach described by Hernán and Robins¹⁹. The study aims to emulate a hypothetical target pragmatic multi-center, non-blinded trial.

Eligibility

Adult inpatients patients (≥ 18 y of age) with culture confirmed proven or probable (see below) invasive monomicrobial GAS in the PINC AI™ database between 2015-2021 who receive a β -lactam for a minimum of 3 days within 3 days of culture will be eligible for inclusion in the emulated trial. Patient will be included if they then receive anti-toxin therapy within 3 days of culture being drawn, as long as B-lactam therapy has been initiated prior or on the same day as antitoxin therapy.

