 - Description: *C. difficile* positive (PCR or antigen) result within same encounter downstream of the antitoxin therapy within 30 days and/or presence of a non present on admission (POA) *C. difficile* diagnosis code in conjunction with receipt of *C. difficile* therapy (PO/rectal vancomycin or PO fidaxomicin or IV metronidazole)

Statistical Analysis Plan

To account for confounding by indication a propensity score (PS) will be generated based on the probability of receiving linezolid using the patient and center level variables. Variables thought to be associated with a clinician's decision to initiate adjunctive treatment with linezolid (vs. clindamycin) and with mortality will be selected for inclusion. Overlap weighting on a propensity-score between the two groups will be performed with downstream adjustment for ICU stay, shock and debridement/source control. To take the clustered data structure into account, matching on center will be attempted if feasible, if not, propensity scores will be calculated using a mixed effects model with hospital as a random effect. Covariate balance between the two groups before and after generation of the weighted cohorts will be assessed by examining the standard mean difference for variables across the exposure categories.

Power calculation

Because no randomized clinical trials have previously compared adjunctive treatment options for GAS, the sample size estimation was derived from the largest retrospective study available³. In that study the overall in hospital mortality in adjunctive clindamycin group 6.5% in the propensity matched cohort. A published abstract, the only other published clinical data on the topic, found mortality between linezolid (n=26) and clindamycin (n=26) groups to be similar (clindamycin 11.5% and linezolid 7.7%)²¹. This was confirmed by preliminary exploration of GAS blood stream infection cases in our dataset (clindamycin 10%, linezolid 12%).

Based on a mortality rate of 6.5% in the both groups as the most conservative estimate and a noninferiority margin of 5% with 1:4 allocation ratio, 1035 patients (828 clinda + 207 Linezolid) will be needed in total to achieve 80% power with a 2-sided α level of 0.05, allowing for 10% dropout. A 5% noninferiority margin was chosen as the maximal difference in mortality between treatments that would be clinically acceptable, by consultation with infectious disease, critical care specialists within the study team.

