Statistical analysis will be performed with R using Rstudio V2022.12.0.353 (R Foundation for Statistical Computing, Vienna, Austria). The reporting of the study will be in line with Strengthening the Reporting of Observational Studies in Epidemiology (STROBE) reporting guidelines²⁰

Sensitivity analysis

The following sensitivity analysis will be performed:

- Analysis of patients with proven GAS only (excluding those with probable GAS)
- Analysis where hospital as a random effect is not included
- An analysis which includes those who receive anti-toxin +/-3 days of index therapy to capture those treated empirically prior to culture results.
- An analysis without PS weighting and only downstream logistical regression (as would be done in a classical observational study).
- An analysis utilizing cloning methodology to account for potential immortal time bias²¹

Subgroup Analysis

We will use similar methods as for the primary analysis to assess the impact of allocation to either treatment group on the following prespecified subgroups

- Patients with NSTI or TSST
- Patients with pressor dependent shock
- Patients admitted to the ICU within one day (+/-) of index GA eligibility culture
- Excluding patients with who received clindamycin that had a clindamycin non-susceptible isolates (defined as resistant or intermediate or a positive D-test)
- Excluding patients with who received clindamycin that had a clindamycin non-susceptible isolates or had clindamycin antimicrobial susceptibility testing missing
- Stratified by days of anti-toxin therapy (>1, >2, >3 days)

Missing Data Plan

Less than 5% missingness across key variables is expected

References

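### The propensity rule, read naturally, leaves out baseline mortality predictors judged unrelated to agent choice: a modest loss of precision, and a confounding risk where that judgment is wrong

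*Combined protocol and SAP*

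**What the plan says.** The Statistical Analysis Plan builds a propensity score for receiving linezolid. A variable qualifies if it is thought to be associated with the clinician's decision to use linezolid rather than clindamycin "and with mortality will be selected for inclusion". Table 1 (Analysis plan, emulation column) describes the inputs as "patient and center level variables selected a priori based on clinical judgment". Neither place lists the variables, and neither says that predictors of mortality alone are added.

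Overlap weighting follows, "with downstream adjustment for ICU stay, shock and debridement/source control". Balance before and after weighting "will be assessed by examining the standard mean difference for variables across the exposure categories"; the variables to be checked, a threshold and a remedy are not stated. Among the sensitivity analyses is "An analysis without PS weighting and only downstream logistical regression", also without a covariate list.

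**The concern.** Overlap weights balance what is in the score. A baseline variable that predicts death but is believed not to steer the choice of agent fails the first half of the rule. Unless it is one of the three downstream terms, nothing in the stated primary analysis brings it in. Age or a comorbidity could be such a variable, if judged unrelated to choice.

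There are two consequences. If the belief is right, the variable is balanced in expectation, but its chance imbalance adds avoidable variance in a study where noninferiority depends on interval width. If the belief is wrong, the variable is a confounder and the risk difference is biased. The background section says clinical experience with linezolid is limited, so beliefs about what drives its use are uncertain. Selecting on relevance to the outcome does not depend on that belief.

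**Working it through.** **1. The plan's own frame.** The Power calculation gives: "Based on a mortality rate of 6.5% in the both groups", "a noninferiority margin of 5% with 1:4 allocation ratio" and "80% power with a 2-sided α level of 0.05", with 10% dropout and 828 + 207 = 1035 patients. With unpooled variance,

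n(clindamycin) = (z_α + z_β)² × p(1−p) × (1 + 4) / margin².

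- One-sided 0.05: (1.645 + 0.842)² × 0.060775 × 5 / 0.0025 = 751.5, so 752 + 188 = 940. Multiplying each arm by 1.10 gives 828 + 207 = 1035, the plan's figure exactly.
- Two-sided 0.05, as written: 955 + 239 = 1194 before dropout. That mismatch is a separate matter; 1035 is used below only to set the scale.

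**2. Scale of the interval.** SE = √[p(1−p)(1/828 + 1/207)], ignoring the effect of weighting.

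- p = 6.5%: SE = 0.01916; 95% half-width 1.96 × 0.01916 = 3.75 points.
- p = 11% (between the 10% and 12% seen in the plan's preliminary data): SE = 0.02431; half-width 4.77 points.

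**3. Belief right: precision only.** First a simple model: N = 1035, 20% linezolid, no true effect, 3000 replicates, one confounder always in the score, and one binary predictor Z left out or put in. Assumed, not from the documents: Z prevalence 30%, and odds ratio of Z on death 3 or 8. There is no downstream adjustment in this model.

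| Z on death | SD, Z out | SD, Z in | Variance ratio | SE larger by |
|---|---|---|---|---|
| OR 3 | 0.0205 | 0.0203 | 1.021 | √1.021 − 1 = 1.0% |
| OR 8 | 0.0199 | 0.0192 | 1.081 | √1.081 − 1 = 4.0% |

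Bias was about zero either way. Noninferiority power at one-sided 0.025 moved from 0.69 to 0.71 and from 0.70 to 0.74.

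The downstream terms must be included for a fair size. With three strong severity predictors in both the score and the weighted outcome model, and five further mortality predictors in or out of the score (combined log-odds SD 0.7, 1.0, 1.5), adding the five cut the SE by 0.8%, 2.5% and 5.8% at 6.5% mortality, and by 2.4%, 3.2% and 7.2% at 11%. If each omitted predictor is instead assumed to correlate 0.4 with the severity behind the downstream terms, the cuts were 0.5-1.7% and 0.5-2.4%. A central reading is 1-4% at 6.5% and up to about 7% at 11%.

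On the half-widths in step 2, 1-4% of 3.75 is 0.04 to 0.15 points, and 7% of 4.77 is 0.33 points.

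**4. Belief wrong: bias.** Same simple model, with Z also related to choice. Bias is in percentage points of risk difference, linezolid minus clindamycin.

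| Z on linezolid | Z on death | Weighted SMD of Z | Bias, Z out | Bias, Z in |
|---|---|---|---|---|
| OR 1.5 | OR 3 | 0.19 | +0.65 | −0.05 |
| OR 2 | OR 8 | 0.34 | +2.20 | −0.08 |
| OR 0.67 | OR 3 | −0.18 | −0.62 | +0.04 |
| OR 0.5 | OR 8 | −0.28 | −1.92 | +0.03 |

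Hand check of the first row: the arms differ in Z by 0.191 × √(0.3 × 0.7) = 0.0875. With 6.5% overall mortality and OR 3, risks are 4.25% without Z and 11.75% with it, a gap of 7.5 points. Then 0.0875 × 7.5 = 0.66 points, in agreement.

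With the downstream adjustment included, five omitted predictors (log-odds SD 1.0 on death, 0.3 on choice) gave +1.9 points at 6.5% mortality and +2.9 at 11%, against about zero when they were in the score. The range 0.6 to 2.9 is 0.6/5 = 12% to 2.9/5 = 58% of the margin.

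The sign matters. Where the omitted factor makes linezolid less likely, the bias favours linezolid and makes a noninferiority conclusion easier: in the third row the chance of concluding noninferiority was 0.82 with Z out and 0.72 with Z in.

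**The case against.** The strongest case on the other side has five parts.

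- **The text does not say only.** It says which variables will be selected, not that others are barred, and Table 1 speaks more broadly of clinical judgment. This stands in part: with no list, no particular omission can be shown. But the conjunctive rule is the only selection criterion that names what a variable must be related to, and nothing adds mortality-only predictors.
- **Severity is already covered.** The downstream terms are plausibly strong predictors of death and enter whatever their link to choice. This stands. It shrinks the gain, most of all if omitted predictors track severity, but does not remove it.
- **Chance imbalance is not a flaw.** With 207 against 828 patients, the SD of a chance SMD is √(1/207 + 1/828) = 0.078, so a predictor truly unrelated to choice exceeds 0.1 in size about 20% of the time. A reader might infer that the comparison is thereby compromised. It is not: such imbalance occurs in any comparison of this size, and the confidence interval already reflects it.
- **Confounding is hypothetical.** It needs a wrongly judged variable, and none is named. This stands, so the bias figures are conditional. The SMD check and the regression-only analysis are partial safeguards, because neither states its variables.
- **Adding terms is not free.** About 0.065 × 207 ≈ 13 deaths are expected on linezolid, and the score may also carry a hospital random effect. This stands as a limit on the length of the list.

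**Conclusion.** The point holds in a limited form. On the natural reading of the rule, baseline mortality predictors judged unrelated to agent choice, other than the three adjusted downstream, are left out of the primary comparison. If the judgment is right there is no bias, and the standard error is roughly 1-4% larger at 6.5% mortality and up to about 7% larger at 11%. If it is wrong, the illustrative bias is 0.6 to 2.9 points in size, in either direction, against the 5-point margin. The confounding risk is the weightier part, and it is conditional.

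All effect sizes, the prevalence of Z and its correlation with severity are assumptions; the documents give none of them. The lower end of the bias range comes from the model without downstream adjustment.

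Two stronger conclusions are tempting. One is that all mortality predictors are left unbalanced, or that the primary result is biased: the downstream adjustment and the absence of a covariate list rule out saying so. The other is that a large number of patients' worth of precision is being given away for nothing: that requires ignoring the downstream adjustment or taking the most favourable effect sizes, and it overlooks the limit on model terms. Choosing believed confounders is a recognised strategy; selecting on the outcome is the more robust and efficient one. The point is a cheap improvement.

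**What to change.** Reword the selection sentence in the Statistical Analysis Plan, and align Table 1 with it, to this effect: pre-specified baseline variables, measured on or before anti-toxin start, that are thought to predict in-hospital death or hospice discharge enter the propensity score whether or not they are thought to influence the choice of agent. Variables thought to influence choice only stay out. List the variables, and report SMDs before and after weighting for all of them.

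The cost is a sentence, a covariate list and a few more terms in a model already planned, drawing on baseline data in the same database. The one downside is that the list must be held to a number of terms that about 207 linezolid patients can support, so it should be a chosen set of the main predictors rather than every candidate.

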Proven and probable invasive GAS definitions will be adapted from the CDC ABCs case definition (<https://www.cdc.gov/abcs/methodology/case-def-ascertain.html>) using a previously used algorithm compatible with EHR data which incorporates ICD-codes³. Proven invasive GAS infection will be defined as GAS isolated from a normally sterile site, such as blood, cerebrospinal fluid, pleural fluid, peritoneal fluid, pericardial fluid, bone, joint/synovial fluid, or internal body site (e.g., lymph node, brain) OR GAS isolated from a wound culture and accompanied by necrotizing fasciitis or streptococcal toxic shock syndrome. Probable invasive GAS infection is defined as the isolation of GAS from a non-sterile site in patients with either an ICD-10 code that matches the clinical infection syndrome (eg ICD-10 for lower respiratory infection and BAL culture with GAS) or a non-specific streptococcal infection code. These include lower respiratory, musculoskeletal, genitourinary and/or skin and soft tissue samples as well other miscellaneous deep-seated infections (eg retropharyngeal abscess). Previously identified ICD-9 codes³ will be cross walked to ICD-10 codes manually with additional manual de-novo search for compatible ICD-10 codes. Final codes and culture site classification will be adjudicated by two infectious diseases clinicians.

Inclusion Criteria

- Adult inpatients patients (≥ 18 y of age)
- Monomicrobial Group A streptococcus invasive infection
- Primary therapy with a B-lactam agent (initiated before or on same day as adjunctive anti-toxin therapy)

Exclusion Criteria

Patient will be excluded if they have any of the following :

- Patients with a polymicrobial GAS culture
- Patients who allocated to the linezolid arm but have a documented linezolid resistant isolate
- Patient with concomitant MSSA/MRSA invasive infection (+/- seven days of index GAS eligibility culture)
- Patients who receive both anti-toxin agents (violation of protocol)
- Patient who don't complete at least 3 days of B-lactam (violation of protocol)

Primary Outcome measure:

in-hospital mortality defined as death during hospitalization or discharge to hospice.

Secondary outcome measures:

- Length of stay among survivors

- *Clostridioides difficile* infection

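### The 6.5% planning mortality is presented as the cautious choice, but of the five rates quoted it is the least conservative for an absolute 5-point margin

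*Combined protocol and SAP*

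**What the plan says.** The Power calculation section of the SAP draws on three sources of mortality data:

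- The largest earlier retrospective study: "overall in hospital mortality in adjunctive clindamycin group 6.5% in the propensity matched cohort".
- A published abstract, which "found mortality between linezolid (n=26) and clindamycin (n=26) groups to be similar (clindamycin 11.5% and linezolid 7.7" (per cent).
- The authors' own "preliminary exploration of GAS blood stream infection cases in our dataset (clindamycin 10%, linezolid 12" (per cent).

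The sample size is then set "Based on a mortality rate of 6.5% in the both groups as the most conservative estimate". The margin is 5%, described as the largest acceptable difference in mortality, so it is absolute. Allocation is one linezolid to four clindamycin, alpha is stated as two-sided 0.05, and 10% dropout is allowed for. The result is that "1035 patients (828 clinda + 207 Linezolid) will be needed in total to achieve 80% power". No power or sample size is shown at any other rate, and nothing elsewhere in the document qualifies the label.

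**The concern.** In a sample-size argument, a conservative input is one that guards against too small a study. For a difference in proportions with a fixed absolute margin, the variance drives the sample size, and the variance increases with the event rate up to 50%. A low rate is therefore the favourable assumption. A low rate would be cautious if the margin were relative, or if the study were driven by event counts, but this margin is neither.

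As written, the reader takes 80% power as a floor with respect to the event rate. Among the plan's own quoted rates it is the ceiling. In a noninferiority comparison, lost power means an inconclusive result. The 10% and 12% also come from the database that is to be analysed, so they cannot simply be set aside. In addition, the primary outcome counts discharge to hospice as death, and the Power calculation does not say whether the 6.5% does so too.

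**Working it through.** **Inputs.** All are from the Power calculation section: margin 0.05 absolute; the same rate p in both arms; clindamycin to linezolid 4:1; 80% power; 10% dropout; 828 + 207 = 1,035. Losing 10% leaves about 745 + 186 evaluable (0.9 × 828 = 745.2; 0.9 × 207 = 186.3).

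**Step 1: reproduce 1,035.** With the unpooled normal formula, the linezolid arm needs

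n = (z₁₋α + z₀.₈₀)² × p(1−p) × (1 + 1/4) / 0.05².

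At one-sided 0.05 and p = 0.065:

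n = (1.645 + 0.842)² × 0.065 × 0.935 × 1.25 / 0.0025 = 187.9 → 188.

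Then 188 × 1.1 = 206.8 → 207, and 207 × 4 = 828, total 1,035. Both arms and the total match, which also confirms that the margin was treated as absolute. At the stated two-sided 0.05 (one-sided 0.025), the same steps give 238.5 → 239 → 263 and a total of 1,315. That mismatch is a separate issue and is not counted here. One-sided 0.05 is used below because it is the alpha that gives the plan's number.

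**Step 2: direction.** In this formula p enters only through p(1−p), so the ratio of sample sizes between two rates does not depend on alpha.

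**Step 3: size.** Power at the planned N is Φ(0.05/SE − 1.645), with SE = √[p(1−p)(1/n_clindamycin + 1/n_linezolid)]. For example, at p = 0.10 with 745/186, SE = 0.0246, 0.05/SE = 2.033, and power = Φ(0.388) = 65%. Changing only the common rate:

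| Common rate | Source | p(1−p) | Relative N | N by the steps above | Power, 745/186 | Power, 828/207 |
|---|---|---|---|---|---|---|
| 6.5% | earlier study, clindamycin | 0.0608 | 1.00 | 1,035 | 80% | 83% |
| 7.7% | abstract, linezolid | 0.0711 | 1.17 | 1,210 | 74% | 78% |
| 10% | own bloodstream data, clindamycin | 0.0900 | 1.48 | 1,535 | 65% | 69% |
| 11.5% | abstract, clindamycin | 0.1018 | 1.67 | 1,735 | 61% | 65% |
| 12% | own bloodstream data, linezolid | 0.1056 | 1.74 | 1,800 | 59% | 63% |

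**Step 4: checks.**

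- *Exact enumeration of the Wald test* at one-sided 0.05 gives 77.6–80.4% at 6.5%, 64.4–68.3% at 10% and 59.1–62.8% at 12%. The formula is up to about 3 points optimistic at 6.5%; the ordering is unchanged.
- *Farrington–Manning formula:* the N ratios against 6.5% are 1.35 at 10% and 1.53 at 12%. They are smaller than in the table but in the same direction.
- *Stated two-sided 0.05:* power is 70–74% at 6.5%, 53–57% at 10% and 47–51% at 12%. The shortfall at 6.5% belongs to the alpha issue.
- *Interval half-width at 12%:* at 90% confidence, 4.15 points (828/207) to 4.38 (745/186), inside the margin; at 95%, 4.95 to 5.22, about equal to it.

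**The case against.** The strongest reply is that 6.5% is the best-supported input. It comes from the largest study, and the Eligibility section takes its case definitions from the same reference, "using a previously used algorithm compatible with EHR data which incorporates ICD-codes". The rivals are weak. The 10% and 12% are preliminary and cover bloodstream infection only, whereas eligibility extends to probable infection from non-sterile sites. The 11.5% and 7.7% are 3 and 2 deaths among 26 patients, with exact 95% intervals of 2.4–30.2% and 0.9–25.1%. The section cites these figures to show that the arms are similar, not as planning rates. All of this stands. It supports 6.5% as a base case; it does not make 6.5% conservative.

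A second reply is that the label has little effect. The records already exist, 1,035 is a number needed rather than a cap, and the final confidence interval will show the precision achieved. This limits the consequence, and power would be higher if more than 1,035 patients are eligible. But the documents do not give the eligible number, so the stated power is all a reader has for now.

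A third reply is that a conservative estimate can simply mean a low one. In a sentence that justifies a sample size, that reading is weak.

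Finally, strict proportionality to p(1−p) belongs to the unpooled formula, and the SAP names no test. That is correct. It changes the size of the effect and leaves its direction alone.

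**Conclusion.** The concern holds. Of the five rates quoted, 6.5% gives the smallest sample size and the highest power, so the label is reversed. At 1,035 and one-sided 0.05, power falls from 80–83% at 6.5% to 65–69% at 10% and 59–63% at 12%. The chance of missing noninferiority is then about 31–41% at 10–12%, against the planned 20%.

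This rests on an absolute margin, equal true mortality in the two arms (an ordinary planning assumption), exactly 1,035 patients, and evaluable numbers between 745/186 and 828/207. The figures are unweighted and make no allowance for overlap weighting or hospital clustering. The direction does not depend on which alpha is adopted.

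The error lies in the label and the caution it implies, not in choosing 6.5%. It should be fixed, but it alters no estimand, margin or analysis.

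**What to change.** In the Power calculation section, delete the words that call 6.5% the most conservative estimate and describe it as the base case. Add one sentence or a short table row giving power at 1,035, or at the eligible number once known, for equal mortality of 6.5, 7.7, 10, 11.5 and 12%, at whichever alpha is adopted. Note beside it that 10% and 12% are from bloodstream infections only and that 11.5% and 7.7% rest on 26 patients per arm. If interval half-widths are added, give them at the matching confidence level, with and without the 10% loss.

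The cost is one deleted phrase and one added sentence or row. No extra patients are needed. The only downside is a less favourable stated power at the higher rates.

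### The planned 1,035 patients give about 70% power at the stated two-sided alpha of 0.05, not 80%; the figure matches a one-sided 0.05 calculation

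*Combined protocol and SAP*

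**What the plan says.** The Power calculation section of the Statistical Analysis Plan contains the document's only sample size statement. Its inputs are:

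- **Event rate:** "Based on a mortality rate of 6.5% in the both groups as the most conservative estimate".
- **Margin and allocation:** "a noninferiority margin of 5% with 1:4 allocation ratio". The plan describes the margin as absolute: "A 5% noninferiority margin was chosen as the maximal difference in mortality between treatments that would be clinically acceptable".
- **Power and alpha:** "80% power with a 2-sided α level of 0.05".
- **Loss:** "allowing for 10% dropout".
- **Result:** "1035 patients (828 clinda + 207 Linezolid) will be needed in total to achieve 80% power with a 2-sided α level of 0.05".

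The endpoint is binary: in-hospital death or discharge to hospice (Primary Outcome measure). The section names no formula, test or software routine for the calculation. Neither the protocol text nor the SAP states the confidence level, or a one-sided alpha, for the noninferiority decision.

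**The concern.** A noninferiority comparison uses only one bound of the confidence interval. A two-sided alpha of 0.05 therefore corresponds to the 95% interval and a one-sided error of 0.025. The printed total looked too small for that level and close to what one-sided 0.05 would give.

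The consequence depends on which interval is eventually used:

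- If noninferiority is judged on the 95% interval, the comparison has less power than stated, and an inconclusive result could be read as coming from an 80%-powered study.
- If it is judged on the 90% interval that the sample size fits, the chance of wrongly declaring noninferiority on a mortality endpoint is 5%, twice the 2.5% that the stated alpha implies.

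Because the decision interval is not written down, the choice between these could be made after the results are known.

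**Working it through.** **Inputs** (all from the Power calculation section): p = 0.065 in both arms, so the true difference is 0; margin 0.05; four clindamycin patients per linezolid patient; 80% power, z = 0.8416; 10% dropout.

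**Formula** (normal approximation, unpooled variance), for the linezolid arm:

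n = (z_α + z_β)² × p(1 − p) × (1 + 1/4) / margin²

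Here p(1 − p) = 0.065 × 0.935 = 0.060775, and 0.060775 × 1.25 = 0.075969.

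**Step 1. Reproducing the printed figure.** With one-sided 0.05, z_α = 1.6449:

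- (1.6449 + 0.8416)² = 6.183
- n = 6.183 × 0.075969 / 0.0025 = 187.9 linezolid, total 939 evaluable
- 187.9 × 1.10 = 206.7, rounded to 207; 4 × 207 = 828; total 1,035

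Both arms match exactly. Dividing by 0.90 instead gives 939.4 / 0.90 = 1,044.

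**Step 2. The stated alpha.** With one-sided 0.025, z_α = 1.9600:

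- (1.9600 + 0.8416)² = 7.849
- n = 7.849 × 0.075969 / 0.0025 = 238.5 linezolid, total 1,192.5 evaluable
- With 10% loss: 1,192.5 / 0.90 = 1,325 (265 + 1,060), or 1,192.5 × 1.10 = 1,312

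Rounding each arm up first (239 + 956 = 1,195) gives 1,328 after loss, which is immaterially different. Against 1,325, the printed total is (1,325 − 1,035) / 1,325 = 22% short.

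**Step 3. Power of the printed sample size.** Power = Φ(0.05 / SE − z_α), with SE = √[0.060775 × (1/n_L + 1/n_C)].

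| Evaluable (linezolid + clindamycin) | SE | Power, one-sided 0.025 | Power, one-sided 0.05 |
|---|---|---|---|
| 186 + 745 (after 10% loss) | 0.02021 | 69.7% | 79.7% |
| 207 + 828 (no loss) | 0.01916 | 74.2% | 83.3% |

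A simulation of the unpooled bound at one-sided 0.025 gave 68.0% and 72.5% for the same two rows.

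**Step 4. Margin that the printed sample size supports.** At 186 + 745 and one-sided 0.025, 80% power requires a margin of 2.8016 × 0.02021 = 0.0566, about 5.7 points.

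**Step 5. Other methods at the stated alpha.** All totals are evaluable patients, before dropout:

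| Method | Total |
|---|---|
| Unpooled with continuity correction | 1,315 |
| Farrington-Manning, linezolid as test arm | 1,564 |
| Two one-sided tests with the type II error split | 1,596 |
| Superiority, 11.5% vs 6.5% | 1,500 |

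Every one exceeds 1,035. Two other routes come near it. Farrington-Manning with the larger arm as the test arm gives 917 evaluable, or 1,009 to 1,019 with dropout. That is not a match, and it reverses the roles of the printed arms. A continuity-corrected superiority test of 1.5% against 6.5% gives 1,050 to 1,061 with dropout, but that is not a noninferiority design and contradicts the equal 6.5% rates.

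**The case against.** Four points can be made for the plan.

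1. **The cause is inferred.** No formula is given, and the exact match also needs an assumed dropout step of × 1.10. This is fair: one-sided 0.05 is the best explanation rather than a documented fact. The shortfall in Step 2 does not depend on it.

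2. **70% is the lower figure.** The outcome is in-hospital, the data are retrospective, and the Missing Data Plan expects under 5% missingness, so the real loss may be below 10%. Power would then lie between 70% and 74%. But 10% is the plan's own allowance, and no value in that range reaches 80%. The × 1.10 step is worth only about 10 patients at the sample size used, and is a minor matter.

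3. **The cohort is not recruited to a target.** It consists of whoever qualifies in the 2015–2021 database, possibly more than 1,035, and the effect estimate and its interval are unaffected by this sentence. That is true, and it is why no enrolment change is asked for. The sentence still tells readers what a cohort of that size can establish, and on its own inputs it is wrong.

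4. **The plan never says that the 95% interval decides.** Correct, but a two-sided alpha of 0.05 implies it, and nothing in the document supports a one-sided 0.05 rule. The silence adds to the problem, because it leaves the error rate of the primary conclusion open.

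**Conclusion.** The concern holds. On the plan's own inputs, 80% power at two-sided 0.05 needs about 1,193 evaluable patients and about 1,325 with 10% loss. The stated 1,035 gives 69.7% power after that loss and 74.2% without it.

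This rests on the unpooled normal approximation, equal mortality of 6.5% and simple unweighted proportions. These are lenient assumptions. The Farrington-Manning test with linezolid as the test arm would have about 54% power at 186 + 745. The formula also leaves out any loss of precision from overlap weighting and hospital clustering, both part of the planned analysis. The section itself reports 10% and 12% mortality in the dataset's bloodstream cases. At 10% in both arms, SE = √[0.09 × (1/186 + 1/745)] = 0.02459, and power at the stated alpha is about 53%. The 70% figure is therefore not pessimistic.

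**What to change.** Correct the sample size sentence and add the missing decision rule:

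- State that noninferiority is judged on the two-sided 95% confidence interval for the mortality difference (one-sided 0.025), which is what the stated alpha means.
- Then give **either** about 1,325 patients (265 linezolid + 1,060 clindamycin) for 80% power with 10% loss, **or** keep 1,035 and report about 70% power after 10% loss (74% if all are evaluable).
- Name the formula, and apply dropout by dividing by 0.90.

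If the sponsor did intend one-sided 0.05, the plan should say so openly, state the 90% interval, justify it for a mortality endpoint and remove the two-sided 0.05 wording.

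The cost is a short text change with no additional patients or data. The only price is a less favourable stated power.
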